8.3.2. Pregnancy

Collection of pregnancy information

Male participants with partners who become pregnant

- The investigator will attempt to collect pregnancy information on any male participant's female partner who becomes pregnant while the male participant is in this study. This applies only to male participants who receive study intervention.
- After learning of a pregnancy in the female partner of a study participant, the investigator
 - will request a consent or assent to release information from the pregnant female partner directly, and
 - within 24 hours after obtaining this consent or assent, will record pregnancy information on the appropriate form and submit it to the sponsor.

The female partner will also be followed to determine the outcome of the pregnancy. Information on the status of the mother and child will be forwarded to the sponsor. Generally, the follow-up will be no longer than 6 to 8 weeks following the estimated delivery date. Any termination of the pregnancy will be reported regardless of gestational age, fetal status (presence or absence of anomalies), or indication for the procedure.

Female participants who become pregnant

- The investigator will collect pregnancy information on any female participant who becomes pregnant while participating in this study. The initial information will be recorded on the appropriate form and submitted to the sponsor within 24 hours of learning of a participant's pregnancy.
- The participant will be followed to determine the outcome of the pregnancy. The investigator will collect follow-up information on the participant and the neonate, and the information will be forwarded to the sponsor. Generally, follow-up will not be required for longer than 6 to 8 weeks beyond the estimated delivery date. Any termination of pregnancy will be reported, regardless of gestational age, fetal status (presence or absence of anomalies), or indication for the procedure.
- While pregnancy itself is not considered to be an AE or SAE, any pregnancy complication or elective termination of a pregnancy for medical reasons will be reported as an AE or SAE.
- A spontaneous abortion, occurring at <20 weeks gestational age, or still birth, occurring at ≥20 weeks gestational age, is always considered to be an SAE and will be reported as such.
- Any post-study pregnancy-related SAE considered reasonably related to the study intervention by the investigator will be reported to the sponsor as described in Section 8.3.1. While the investigator is not obligated to actively seek this information in former study participants, they may learn of an SAE through spontaneous reporting.
- Any female participant who becomes pregnant while participating in the study will discontinue study intervention. If the participant is discontinued from the study, follow the standard discontinuation process and continue directly to the follow-up phase. The follow-up on the pregnancy outcome should continue independent of intervention or study discontinuation.

Prior to continuation of study intervention following pregnancy, the following must occur:

- The sponsor and the relevant institutional review board/independent ethics committee (IRB/IEC) give written approval.
- The participant gives signed informed consent (or assent, as applicable).
- The investigator agrees to monitor the outcome of the pregnancy and the status of the participant and the participant's offspring.

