The primary clinical question of interest is: What is the intervention effect in percentage of participants achieving EASI-75 after 16 weeks of lebrikizumab 250 mg once every 2 weeks (Q2W) intervention in participants with moderate-to-severe AD, who have been previously treated with dupilumab and who remain on study treatment until Week 16.

The estimand is described by the following attributes:

Population: participants with moderate-to-severe AD who have been previously treated with dupilumab and who remain on study treatment until Week 16.

Further details can be found in Section 5.

Endpoint: Do participants achieve at least 75% improvement from baseline to Week 16 in EASI.

Intercurrent events: There are no intercurrent events for this population since participants who initiate rescue medication are discontinued from the study and hence study treatment. Therefore, participants who stay on study treatment through Week 16 will not have an intercurrent event such as initiating rescue medication or permanently discontinuing treatment.

Population-level summary: Percentage of participants achieving EASI-75 response at Week 16.

Secondary estimand(s)

There is no secondary estimand planned at this stage, however, additional estimand(s) might be specified in the statistical analysis plan (SAP).

Overall Design

Study J2T-MC-KGBO (KGBO) is an open-label, Phase 3b study, which is 24 weeks in treatment duration. The study is designed to evaluate the safety and efficacy of lebrikizumab in adults and adolescents (≥ 12 years to < 18 and weighing ≥ 40 kg) with moderate-to-severe AD and previously treated with dupilumab.

During the 24-week Treatment Period, approximately 120 participants will receive treatment:

- 500 mg subcutaneous (SC) once every 2 weeks (Q2W) loading dose at baseline and Week 2, followed by 250 mg SC Q2W until Week 16.
- Responders, defined as achieving IGA (0,1) or EASI-75 at Week 16, will receive 250 mg SC once every 4 weeks (Q4W).
- Inadequate responders at Week 16 will continue to receive 250 mg SC Q2W.

Brief Summary:

The purpose of this study is to determine the proportion of participants achieving EASI-75 at Week 16 with lebrikizumab in participants with moderate-to-severe AD previously treated with dupilumab.

Study details include:

- The planned study duration will be up to 38 weeks.
- The treatment duration will be up to 24 weeks.

- The visit frequency will be every 2 weeks for the first 2 visits, then every 4 weeks thereafter.

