7.1. Discontinuation of Study Intervention

When necessary, a participant may be permanently discontinued from study intervention. If so, the participant will remain in the study to complete procedures for an early discontinuation visit and post-treatment follow-up, if applicable, as shown in the SoA.

A participant should be permanently discontinued from study intervention if

- the participant becomes pregnant during the study
- in the opinion of the investigator, the participant should permanently discontinue the study intervention for safety reasons
- the participant develops a malignancy, except for successfully treated basal or squamous cell skin carcinoma
- the participant tests positive for HBV DNA (see Section 8.2.3)
- the participant tests positive for HCV RNA (Section 8.2.4)
- if the participant experiences a hepatic event or liver test abnormality as specified in the liver chemistry stopping criteria (see Section 7.1.1)
- the participant develops HIV infection
- the participant requires rescue medication treatment for symptoms of AD in the treatment period
- the participant develops any infection that is opportunistic, such as active tuberculosis and other infections whose nature or course may suggest an immuno-compromised status, and
- the participant has an AE or an SAE or a clinically significant change in a laboratory value that, in the opinion of the investigator, merits discontinuation of study intervention and appropriate measures being taken.

Hepatitis

- prior to discontinuation of any immunomodulatory and/or immunosuppressive therapy due to hepatitis, including study intervention, the participant is to be referred to, evaluated, and managed by a specialist physician with expertise in evaluation and management of viral hepatitis.
- the timing of discontinuation from study intervention relative to the initiation of any antiviral treatment for hepatitis is to be based on the recommendation of the consulting specialist physician, in conjunction with the investigator, and aligned with medical guidelines and standard of care.

Hypersensitivity

- if the investigator determines that a systemic hypersensitivity reaction has occurred related to study intervention administration, the participant may be permanently discontinued from the study intervention, and the sponsor's designated medical monitor

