7.1.2. Temporary Discontinuation of Study Intervention

Temporary withholding of study intervention is required if the participant meets any of the following infection-related criteria during the study:

- Serious or opportunistic infections, as defined in Section 5.2. Study intervention is to be withheld until resolution of all acute clinical signs and symptoms, and completion of all appropriate anti-infective treatment.
- HBV DNA results that are reported as positive, or as detecting HBV DNA, but HBV DNA is below the level of quantification. In this situation, the sponsor's designated medical monitor should be contacted regarding the participant's status. HBV DNA testing is to be repeated as soon as is feasible. If HBV DNA is confirmed as positive, the participant must be permanently discontinued from study intervention as described in Section 7.1.
- If a participant <18 years of age loses a clinically significant amount of weight (below 40 kg), the investigator should assess rationale for weight loss and use clinical judgment to determine if the participant should temporarily discontinue the treatment.

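### Protocol 7.1 makes the stop for pregnancy permanent, but 8.3.2 sets conditions for continuing study drug: the sections conflict on whether dosing may resume

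*Protocol*

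**What the plan says.** Protocol 7.1 introduces its list with "A participant should be permanently discontinued from study intervention if", and the first item is "the participant becomes pregnant during the study". No exception is attached, and the item does not point to 8.3.2.

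Protocol 8.3.2, under female participants, states: "Any female participant who becomes pregnant while participating in the study will discontinue study intervention". The word permanent does not appear there. The section then continues: "Prior to continuation of study intervention following pregnancy, the following must occur". Three conditions follow:

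- "The sponsor and the relevant institutional review board/independent ethics committee (IRB/IEC) give written approval";
- the participant signs consent, or assent where that applies;
- "The investigator agrees to monitor the outcome of the pregnancy and the status of the participant", and likewise that of her offspring.

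Protocol 7.1.2, which covers temporary withholding, does not mention pregnancy.

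**The concern.** A stop that is permanent and a procedure for continuing afterwards do not fit together. When a test is positive, the site needs one instruction. As written, one investigator could treat study drug as finished under 7.1, and another could apply to continue it under 8.3.2. Each could cite the protocol.

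Elsewhere the protocol keeps dosing and pregnancy apart. Exclusion criterion 43 bars participants who are pregnant or planning pregnancy. Inclusion criterion 9 requires abstinence or highly effective contraception for women of child-bearing potential, to at least 18 weeks after the last dose. The Schedule of Activities places local urine tests before dosing. The instruction for what happens when those measures fail should be equally clear. What is at stake is participant safety and consistent conduct across sites.

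**Working it through.** No figure is involved, so the check is a comparison of the text.

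| Question | Protocol 7.1 | Protocol 8.3.2 |
|---|---|---|
| Does study drug stop when a participant becomes pregnant? | Yes | Yes |
| Is the stop called permanent? | Yes | Not stated |
| Is there a route back to dosing? | None given for pregnancy | Yes, on three conditions |
| Does it refer to the other section? | No | No |

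**Step 1: the immediate action.** The first row shows agreement. A site following either section stops dosing when pregnancy occurs.

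**Step 2: resumption.** The second and third rows show the conflict. It also appears within 8.3.2, where one bullet stops the drug and the next paragraph sets terms for continuing it.

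**Step 3: could pregnancy be a temporary stop?** Section 7.1.2 is where reversible stops are listed, and it opens with "Temporary withholding of study intervention is required if the participant meets any of the following infection-related criteria during the study". Its items are serious or opportunistic infection, detectable hepatitis B DNA below the level of quantification, and clinically significant weight loss in participants under 18. Pregnancy is absent. It appears only on the permanent list.

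**Step 4: what does *following pregnancy* mean?** Two readings are open.

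- *After the pregnancy has ended.* The bare words allow this. It still conflicts with a permanent stop. It also fits awkwardly with the third condition, since agreeing to monitor an outcome suggests that the outcome is not yet known. The synopsis says "The treatment duration will be up to 24 weeks", and pregnancy is excluded at entry, so a pregnancy carried to term would not end within the treatment period. One that ended early could.
- *After the pregnancy has been identified, while it continues.* The third condition leans this way, but the section does not say so.

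The text does not settle which reading is intended. Fetal exposure follows only from the second.

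**Step 5: is there reconciling text elsewhere?** The discontinuation, temporary withholding, eligibility and pregnancy sections contain none. Protocol 6.6 refers to dosing after Week 24 under a separate addendum. That addendum is not among the documents and could not be checked.

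**The case against.** The strongest reply is that this is a missing cross-reference and not two opposed rules. Section 7.1 says *should*. Its liver item points to 7.1.1, where drug is interrupted and resumption can be considered with the medical monitor. A general list softened by a specific section is therefore a pattern this protocol already uses, and 8.3.2 could be read as the specific section for pregnancy. Resumption is also closely controlled: it needs sponsor and ethics board approval in writing, signed consent or assent, and a monitoring commitment. A site cannot restart dosing on its own authority.

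Much of this stands. It confines the conflict to resumption and makes an uncontrolled restart unlikely. It does not remove the conflict. The liver item carries its pointer and the pregnancy item does not, so a reader of 7.1 has no reason to look for an exception.

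A reader might also infer two stronger claims.

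- *That the protocol permits dosing during an ongoing pregnancy.* The documents do not say this outright. It is one reading of ambiguous wording, and it is subject to the approvals.
- *That the conflict affects the primary analysis, because the primary estimand covers participants who stay on treatment to Week 16.* Both sections stop the drug at once. The difference could matter only if a pregnancy occurred before Week 16, every approval was obtained, and dosing resumed in time. A pregnancy after Week 16 cannot matter for that population. Nothing in the documents suggests an effect on the response rate.

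**Conclusion.** The point holds as an internal inconsistency in a participant-safety instruction. Sections 7.1 and 8.3.2 agree that study drug stops on pregnancy and disagree on whether it may resume. Section 8.3.2 also leaves the timing of any resumption undefined.

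The size is qualitative. The documents give neither a pregnancy rate nor the expected number of women of child-bearing potential, so no count of affected participants can be derived. Cases are likely to be few, given the exclusion, contraception and testing rules; that is a judgement and not a figure from the plan. The sample size, confidence intervals and planned summaries do not depend on this point. It deserves correction because the instruction concerns safety, not because it threatens the results.

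The conclusion rests on the two sections as printed, and on the assumption that no document outside the protocol and SAP already resolves the question.

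**What to change.** Reconcile Protocol 7.1 and 8.3.2 so that one instruction applies once a pregnancy is confirmed, and have each section refer to the other. If any provision for continuation is kept, 8.3.2 should define what *following pregnancy* means, and 7.1 should acknowledge the provision. If none is kept, the conditions in 8.3.2 have no purpose and should be removed. Which of these is right is a clinical and ethical decision for the sponsor and is not proposed here.

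The cost is a wording change in a protocol amendment. Under Protocol 10.1.1 an amendment needs IRB/IEC approval before it is implemented, and health authority approval as well if it counts as substantial, so the change could sensibly be made with the next planned amendment. No change to the SAP is needed.

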8.3.3. Adverse Events of Special Interest

The following TEAEs will be designated AE of special interest (AESI):

- conjunctivitis
- herpes infection or zoster, and
- parasitic infection or an infection-related to an intracellular pathogen.

If these AESIs are reported, sites will be prompted to collect additional data. Participant records must include any follow-up information regarding these AESI. Study intervention should be discontinued if an AE is deemed persistent and if continuation of study intervention would not be in the best interest of the participant. Discuss discontinuation of study intervention with the sponsor or designee prior to implementation.

8.3.3.1. Infections, Including Serious Infections and Opportunistic Infections

Completion of the Infection CRF page is required for each infection reported as an AE or SAE. The sponsor will identify infections considered to be opportunistic based on the article by Winthrop et al. (2015) (Section 10.9, Appendix 9).

8.3.4. Facial Dermatitis

Completion of the facial dermatitis follow-up CRF page is required for each facial dermatitis event reported as an AE or SAE.

8.3.5. Hypersensitivity

Many drugs, including oral agents and biologic agents, carry the risk of systemic hypersensitivity reactions. If such a reaction occurs, additional data should be provided to the sponsor in the designated CRFs.

Sites should have appropriately trained medical staff and appropriate medical equipment available when study participants are receiving study intervention. It is recommended that participants who experience a systemic hypersensitivity reaction be treated per national and international guidelines.

In the case of a suspected systemic hypersensitivity event, additional blood samples should be collected as described in Section 10.2.1. Laboratory results are provided to the sponsor via the central laboratory.

8.3.6. Injection Site Reactions

Symptoms and signs of a local injection site reaction may include erythema, induration, pain, pruritus, and edema.

If an injection site reaction is reported by a participant or site staff, the injection site reaction CRF will be used to capture additional information about this reaction, for example, injection site pain, degree and area of erythema, induration, pruritus, and edema.

8.4. Pharmacokinetics

At the visits and times specified in the SoA, venous blood samples will be collected and stored for potential analysis of serum concentrations of lebrizumab.

Samples will be stored at a facility designated by the sponsor and may be assessed at a later date at a laboratory approved by the sponsor using a validated enzyme-linked immunosorbent assay method.

Instructions for the collection and handling of blood samples will be provided by the sponsor. The actual date and time (24-hour clock time) of each sample and the most recent lebrizumab dose prior to PK blood draw must be recorded.

Sample retention is described in Section 10.1.11. Bioanalytical samples collected to measure investigational product concentrations will be retained for a maximum of 1 year following last participant visit for the study. During this time, samples remaining after the bioanalysis may be used for exploratory analyses such as bioanalytical assay validation or cross-validation exercises.

8.5. Pharmacodynamics

Pharmacodynamic parameters are not evaluated in this study.

8.6. Genetics

A blood sample for DNA isolation will be collected from participants.

See Appendix 10.5 for Information regarding genetic research and Section 10.1.11 for details about sample retention and custody.

8.7. Biomarkers

- Serum samples will be collected to discern responder variability within the study and to track response variability to lebrizumab. Biomarkers will include but not limited to 
 Samples will be collected according to the schedule described in the SoA and as detailed in laboratory manual provided separately to sites.
- The sponsor may store samples according to Section 10.1.11. Additionally, with participants' consent, samples may be used for further research by the sponsor or others such as universities or other companies to contribute to the understanding of AD or other diseases, the development of related or new treatments, or research methods.

8.8. Immunogenicity Assessments

At the visits and times specified in the SoA, venous blood samples will be collected for the purpose of determining antibody production against lebrizumab. To aid interpretation of these results, a blood sample for PK analysis will be collected at the same time points.

All samples for immunogenicity should be taken predose when applicable and possible. Instructions for the collection and handling of blood samples will be provided by the sponsor. The actual date and time (24-hour clock time) of each sample collection will be recorded. Immunogenicity samples will be stored at a facility designated by the sponsor and may be later assessed by a validated assay designed to detect ADAs in the presence of lebrizumab at a laboratory designated by the sponsor. Samples may also be used for the development and control of an immunogenicity assay.

Treatment-emergent ADAs are defined in Section [9.3.6.4](#).

Sample retention is described in Section [10.1.11](#).

8.9. Health Economics

Health economics and/or medical resource utilization will not be collected as part of this study.

9. Statistical Considerations

The SAP will be finalized prior to first participant visit, and it will include a more technical and detailed description of the statistical analyses described in this section. This section is a summary of the planned statistical analyses of the most important endpoints, including primary and key secondary endpoints.

9.1. Statistical Hypotheses

The primary objective is to evaluate efficacy of lebrikizumab 250 mg Q2W on reducing skin sign of AD, measured by percentage of participants who achieve at least 75% improvement in baseline EASI at Week 16 in participants with moderate-to-severe AD who were previously treated with dupilumab. There is no hypothesis testing planned nor inference statistical analysis planned.

9.2. Analyses Sets

Participant Analysis Set	Description
ITT population	All enrolled participants. Participants will be included in the analyses according to the planned intervention.
Safety population	All participants who are exposed to study intervention.

Abbreviation: ITT = intent-to-treat.

9.3. Statistical Analyses

9.3.1. General Considerations

Statistical analysis of this study will be the responsibility of Lilly or its designee. A detailed SAP describing the statistical methodologies will be developed by Lilly or its designee.

Any change to the data analysis methods described in the protocol will require an amendment ONLY if it changes a principal feature of the protocol. Any other change to the data analysis methods described in the protocol, and the justification for making the change, will be described in the CSR. Additional exploratory analyses of the data will be conducted as deemed appropriate.

All analyses will be descriptive. Frequencies, percentages, and 90% CI for percentages will be reported for discrete efficacy endpoints. Mean, standard deviation, minimum, Q1, median, Q3, maximum, and the number of participants will be reported for continuous efficacy endpoints. AEs, discontinuation, and other categorical safety data will be summarized using frequencies and percentage. Continuous vital signs, body weight, and other continuous safety variables including laboratory variables will be summarized descriptively as well.

